456 maintained the list containing the condition information corresponding to each visit during the
457 study in case the blind conditions needed to be revealed in real time (e.g., if participants reported
458 adverse effects during tDCS).

459 *6.3 Stimulation Parameters*

The total stimulation time of 40 minutes was divided into two twenty-minute sessions to allow repeated stimulation, which may increase efficacy (Cheng et al., 2020; Kim et al., 2019). The active stimulation included active current at 2mA, ramping up over 15 seconds, sustaining for 20 minutes, and finally ramping down for 15 seconds. The dimensions of each electrode were 5 × 7 centimeters in size (35 cm^2), which led to a current density of 0.5714 mA/cm². For the sham condition, electrodes were still attached for 20 minutes each session, but the actual stimulation time was limited to 45 seconds per session, with 15 seconds of gradual stimulation, leading up to 15 seconds of full stimulation, and finally 15 seconds of ramping down. This limited stimulation mimicked the ramp up phase of active stimulation, making it more difficult for participants to guess the condition. The machine also automatically performed impedance control checks throughout the neurostimulation to ensure that both the participant and the experimenter could not tell which condition was being administered. Following each session,

472 inquiries into the participants' perceptions of the suspected condition showed that their accuracy
473 in identifying the correct condition was below chance levels (47%), supporting the efficacy of
474 the blinding procedures.

475

476 **Figure 3. Computational simulation of tDCS-induced current density.** (A) shows the
477 montage location in the study (1 = right VLPFC, 2 = left VLPFC). (B) reveals the distribution of
478 the current density estimated based on the stimulation location and parameters.

479

480 6.4 Current Modeling

481 To better characterize the current distribution during the stimulation, current modelling
482 was conducted for the active condition. This computational simulation utilized a finite element
483 model derived from MRI, implemented through the Comets toolbox (Jung et al., 2013) in Matlab
484 (<http://www.COMETStool.com>). **Figure 3** illustrates a detailed three-dimensional (3D)
485 numerical analysis of the current density generated by tDCS based on the montage applied in this

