516 = do not agree, 5 = totally agree). Additionally, the SSPS contains three subscales, measuring
517 paranoid, neutral, and positive thinking. Scores range from 20-100, and higher scores represent
518 higher state paranoid ideation. Acceptable reliability and validity have been demonstrated in
519 previous research in patients with psychosis (Freeman et al., 2015; Veling et al., 2016). In the
520 current study, the total scale (Visit 1: Cronbach's $\alpha_{pre} = 0.819$, Cronbach's $\alpha_{post} = 0.840$; Visit 2:
521 Cronbach's $\alpha_{pre} = 0.798$, Cronbach's $\alpha_{post} = 0.880$) and the persecution subscale scale (Visit 1:
522 Cronbach's $\alpha_{pre} = 0.924$, Cronbach's $\alpha_{post} = 0.926$; Visit 2: Cronbach's $\alpha_{pre} = 0.903$, Cronbach's
523 $\alpha_{post} = 0.911$) showed outstanding internal consistency. The neutral thinking (Visit 1: Cronbach's
524 $\alpha_{pre} = 0.750$, Cronbach's $\alpha_{post} = 0.457$; Visit 2: Cronbach's $\alpha_{pre} = 0.603$, Cronbach's $\alpha_{post} = 0.803$)
525 and positive thinking (Visit 1: Cronbach's $\alpha_{pre} = 0.706$, Cronbach's $\alpha_{post} = 0.731$; Visit 2:
526 Cronbach's $\alpha_{pre} = 0.611$, Cronbach's $\alpha_{post} = 0.853$) subscales showed mostly acceptable internal
527 consistency.

528 **State Anxiety.** Considering that anxiety has been consistently identified as a construct
529 that overlaps with paranoia (Martin & Penn, 2001; Startup et al., 2007), we also measured state
530 anxiety to examine potential changes after tDCS. The State subscale of State-Trait Anxiety
531 Inventory (STAI-S) includes 20 items measuring current feelings (e.g., "I am tense", "I feel
532 nervous") on a four-point Likert scale (1 = not at all, 4 = very much so; scores range 20-80)
533 (Spielberger, 2010), with higher scores indicating higher anxiety at this moment. The STAI-S
534 demonstrated excellent internal consistency in both visits (Visit 1: Cronbach's $\alpha_{pre} = 0.879$,
535 Cronbach's $\alpha_{post} = 0.869$; Visit 2: Cronbach's $\alpha_{pre} = 0.847$, Cronbach's $\alpha_{post} = 0.908$).

536 *7.3 Assessments Between the Two Stimulation Sessions*

537 As noted, participants were asked to sit quietly for 30 minutes after each stimulation

538 session to enable the stimulation to work thoroughly throughout the neural networks. Next, they
539 completed several assessments of basic cognitive function and social cognitive ability/bias that

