540 have been generally linked to psychotic symptoms and paranoia but that were not of primary
541 importance and therefore not reported here. Relationships among paranoia, social decision-
542 making, and aggression were also explored in this segment for secondary analyses. Since these
543 analyses were not the main focus of the project, they are not included in the main text (details of
544 all measures administered between stimulation sessions can be found in **Appendix A**).

545 Participants were offered a 30-minute break before the second stimulation session of that visit.
546 The only measure relevant to the main goal of this study is overall social functioning as detailed
547 below:

548 ***Birchwood Social Functioning Scale (SFS; Stimulation Visit 1 and 2).*** The SFS
549 (Birchwood et al., 1990) measures 7 domains of social adjustment based on self-reports (range =
550 0-223, Cronbach's $\alpha_{\text{visit 1}} = 0.915$, Cronbach's $\alpha_{\text{visit 2}} = 0.897$), including social
551 engagement/withdrawal (range = 0-15; Cronbach's $\alpha_{\text{visit 1}} = 0.422$, Cronbach's $\alpha_{\text{visit 2}} = 0.561$),
552 interpersonal communication (range = 0-9; Cronbach's $\alpha_{\text{visit 1}} = 0.426$, Cronbach's $\alpha_{\text{visit 2}} = 0.269$),
553 prosocial activities (range = 0-66; Cronbach's $\alpha_{\text{visit 1}} = 0.879$, Cronbach's $\alpha_{\text{visit 2}} = 0.815$),
554 recreation activities (range = 0-45; Cronbach's $\alpha_{\text{visit 1}} = 0.684$, Cronbach's $\alpha_{\text{visit 2}} = 0.749$),
555 independence-competence (range = 0-39; Cronbach's $\alpha_{\text{visit 1}} = 0.911$, Cronbach's $\alpha_{\text{visit 2}} = 0.934$),
556 independence-performance (range = 0-39; Cronbach's $\alpha_{\text{visit 1}} = 0.915$, Cronbach's $\alpha_{\text{visit 2}} = 0.920$),
557 and employment (single item; range = 0-10). A higher score on each subscale indicates better
558 functioning in the respective social domain, while a higher overall score signifies better social
559 functioning in general. The SFS was originally developed for schizophrenia patients and has
560 been widely used to measure social functioning outcomes in this population (Birchwood et al.,
561 1990; Burns & Patrick, 2007).

562 *6.7 Stimulation Visits: Post-stimulation Assessments*

563 ***State Paranoia and State Anxiety.*** SSPS and STAI-S were administered as described in
564 the pre-stimulation assessments.

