618 along a 7-point scale, as well as the emotions associated with and perceptions of social
619 interactions since the last survey (e.g., did you interact with anyone since your last survey?).
620 Affective states since the past alarm were rated on a 7-point scale using the following items:
621 sad/depressed, excited, irritated, happy, belongingness, and burden to others. Expectations

622 regarding subsequent interpersonal situations were also rated on a 7-point scale (e.g., how much
623 interest do you have in interacting with people for the rest of the day?). **Appendix B** contains the
624 complete list of EMA questions (i.e., paranoia: Q1; social functioning: Q3, Q4, Q5, Q6, Q7, Q14,
625 Q15). Adherence was monitored remotely via a secure platform, and participants who missed 3
626 consecutive surveys were contacted by research personnel to identify and resolve any issues.
627 Compensation of the EMA periods was determined by the actual number of surveys completed
628 to encourage adherence.

629 A total of 47 (out of 50) participants had full data across three EMA periods. One
630 participant did not have a phone and chose not to participate in the EMA protocol. Two
631 participants completed baseline EMA but lost their phones afterwards, and thus chose not to
632 complete the two remaining EMA periods. EMA compliance in the current study was above 80%
633 across the three periods (EMA1 = 82.74%, EMA2 = 83.38%, EMA3 = 80.04%).

634

635 **9. Statistical Analyses Plan**

636 For all tests, a conventional threshold of $\alpha = 0.05$ was used. While opting not to correct
637 for multiple comparisons may permit alpha inflation, we did not want to risk missing any
638 potential therapeutic effects in this treatment study by increasing the likelihood of Type II errors.
639 Therefore, in line with a large body of existing literature, findings that passed the significance
640 level of $\alpha = 0.05$ are presented.

641 **Hypothesis 1a:** To test the reduction in paranoia measured in the lab (active vs. sham
642 stimulation), repeated-measures ANOVAs were performed for self-reported state paranoia
643 measured both before and after the stimulation, while paired-samples t-tests were performed for
644 paranoia-related outcomes measured only after stimulation (i.e., attributional bias and hostility,
645 trust to strangers).

646 **Hypothesis 1b:** Multilevel modeling (MLM) with maximum likelihood robust estimation was

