647 used to test the differences in daily feelings of paranoia (i.e., Q1) across the three EMA periods
648 (EMA-baseline vs. EMA-active vs. EMA-sham), with the condition of the EMA period being
649 dummy-coded.

650 **Hypothesis 2a:** To test the improvement in social functioning measured in the lab (active vs.
651 sham stimulation), paired-samples t-tests were performed for self-reported social functioning
652 measured only after the stimulation.

653 **Hypothesis 2b:** MLM with maximum likelihood robust estimation was used to test the
654 differences in daily social functioning (i.e., Q3, Q4, Q5, Q6, Q7, Q14, Q15) across the three
655 EMA periods (EMA-baseline vs. EMA-active vs. EMA-sham), with the condition of the EMA
656 period being dummy-coded.

657 Notably, one of the daily social functioning questions (i.e., Q3: Since the past alarm, who
658 have you interacted with?) has a different score range. It is quantified as the frequency of social
659 interactions, where a higher score indicates more interactions across a broader range of people
660 categories (range = 0-5). In contrast, the remaining six items adhere to a score range of 1-7.
661 Therefore, we performed MLM separately for Q3 (named as social interaction frequency) and for
662 the average of items Q4, Q5, Q6, Q7, Q14, and Q15 (named as social interaction motivation and
663 experience) for parsimony.

664

665 **10. Participant Payment**

666 Participants were compensated \$20 for completing the enrollment visit, \$100 for each of
667 the two in-lab stimulation visits, and up to \$16 for each of the 7-day EMA periods (three EMA
668 periods in total), totaling a maximum of \$268. Participants who enrolled in the study but were
669 found ineligible during screening were still compensated \$20. If participants stopped taking part
670 in the study or were withdrawn by the research team, they received \$5 for each 20 minutes
671 completed during the lab visits. For example, if they completed 1 hour of the study, they were
672 paid \$15. Compensation for each EMA period was determined by the number of surveys
673 completed, with \$0.75 paid for each survey except for the final survey, which was worth \$1 (to
674 allow for an even amount of \$16 per EMA period if all 21 surveys were completed). Parking on
675 campus was provided for participants.
676

677 **11. Risk and Benefits Assessments**

678 *11.1 Potential Risks*

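### Hypothesis 2a uses a Social Functioning Scale score taken after one of the visit's two sessions, so its paired test estimates a same-day, one-session effect and not the effect of the two-session condition

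*Combined protocol and SAP*

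**What the plan says.** Section 3 defines each condition as two stimulation sessions at least 3 hours apart. Section 6.3 gives the amount: "The total stimulation time of 40 minutes was divided into two twenty-minute sessions". Hypothesis 2a (Section 3.1) predicts better self-reported social functioning after the active condition than after sham.

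The in-lab measure for this hypothesis is the SFS. It is described under the heading "Assessments Between the Two Stimulation Sessions" (Section 7.3) and entered as "Birchwood Social Functioning Scale (SFS; Stimulation Visit 1 and 2". That block begins after 30 minutes of quiet sitting following stimulation and ends as follows: "Participants were offered a 30-minute break before the second stimulation session of that visit". The SFS is singled out there as the one measure in the block that bears on the main goal. It appears neither in Section 7.2 (pre-stimulation) nor under "Stimulation Visits: Post-stimulation Assessments" (numbered 6.7).

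Section 9, Hypothesis 2a, reads "sham stimulation), paired-samples t-tests were performed for self-reported social functioning", with the outcome described as "measured only after the stimulation". Hypothesis 1a uses nearly the same phrase, "paranoia-related outcomes measured only after stimulation", for attributional bias, hostility and trust. Those measures are in the post-stimulation block.

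Daily-life social functioning is assigned to Hypothesis 2b. It compares three EMA periods with dummy coding, separately for Q3 and for the average of Q4 to Q7, Q14 and Q15.

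**The concern.** Section 9 describes the SFS and the end-of-visit outcomes of Hypothesis 1a in almost the same terms, although one follows a single session and the others follow both. A reader who works from Section 9 would take the SFS result as the response to the full condition.

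The protocol itself treats the number of sessions as important. Section 3 gives two sessions per condition because relief of clinical paranoia may need more than one, and Section 2.5.1 cites a null single-session study in schizophrenia. A null Hypothesis 2a could therefore be reported as two sessions failing to improve social functioning, and a positive one could be credited to both. The SFS score supports neither statement. If the daily-life conclusion then moves to Hypothesis 2b, the scoring of its composite has to be sound.

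**Working it through.** **The plan's own figure.** Section 4.1 gives N = 46. A repeated-measures ANOVA with two measurements has noncentrality N × 2 × f² / (1 − ρ). With f = 0.25 and ρ = 0.3 this is 46 × 2 × 0.0625 / 0.7 = 8.21. On 1 and 45 degrees of freedom at α = 0.05 the power is 0.801, so 46 reproduces (reading the 0.25, printed as β, as Cohen's f). The sample size is not in dispute.

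**Sequence within a stimulation visit** (Sections 7.2, 7.3 and the section numbered 6.7):
1. Pre-stimulation measures, no SFS.
2. First session, 20 minutes.
3. 30 minutes of quiet sitting, then the 7.3 block, which includes the SFS.
4. Break, then second session, 20 minutes.
5. Post-stimulation measures, no SFS.

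At the SFS, 1 of 2 sessions has been given: 20/40 = 50% of the stimulation time.

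**What the paired contrast estimates.** Let D be the same-day effect of one active session on the SFS, and L any effect of active stimulation at Visit 1 still present in the Visit 2 SFS. Assume no period effect and nothing lasting from sham. Section 6.2 gives 26 active-first and 24 sham-first participants.
- Active-first, active minus sham: D − L.
- Sham-first, active minus sham: D.
- Mean: [26(D − L) + 24D] / 50 = D − 0.52L.

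The second session's effect does not enter the score labelled active. For active-first participants, whatever remains of the Visit 1 effect enters the score labelled sham. The Visit 2 SFS does come after the Visit 1 EMA week (visits averaged 14.58 days apart), but it carries the Visit 2 label. No SFS follows the Visit 2 EMA week.

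**Can the loss be sized?** Not from the documents, which give no one-session effect on the SFS. As a range only, take a paired t-test with n = 50, two-sided α = 0.05, d = 0.5 and ρ = 0.3. Power is 0.83 if the whole planned effect is present after one session, 0.59 at 75% of it, 0.31 at 50% and 0.11 at 25%. The fractions are assumptions, and ρ = 0.3 is the planning value, not an observed SFS correlation.

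**SFS content** (ranges in Section 7.3): 15 + 9 + 66 + 45 + 39 + 39 + 10 = 223.
- Prosocial, recreation and independence-performance: 66 + 45 + 39 = 150 (67%).
- With employment: 160 (72%).
- With engagement/withdrawal as well: 175 (78%).

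By name, then, 67–78% of the points concern real-life activity or performance.

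**Q15 in the Hypothesis 2b composite.** Appendix B scores Q15, on wanting to avoid others, with 7 as very much. Higher is worse, whereas higher is better on Q4 to Q7 and Q14. Section 9 averages all six and states no reversal.
- If every item improves by d, the unreversed average moves (5d − d)/6 = 0.67d.
- With equal item variances and inter-item correlation r after correct keying, the variance of the sum is proportional to 6 + 30r when Q15 is reversed and 6 + 10r when it is not.
- Ratio of standardized effects: (4/6) × √[(6 + 30r)/(6 + 10r)]. At r = 0.2 this is 0.82; at r = 0.6 it is 0.94. Both values of r are assumed.

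**The case against.** The best defence is that the Section 9 phrase is true. The SFS does follow stimulation, and the phrase mainly marks the absence of a pre-measure, which is why a t-test replaces the repeated-measures ANOVA. Section 7.3 discloses the placement under an explicit heading. Hypothesis 2a is already confined to in-lab self-report, with daily life left to Hypothesis 2b. The planning effect, d = 0.51, also came from a single-session pilot (Sections 2.5.3 and 4.1), although that pilot concerned subclinical paranoia in students. All of this stands. It makes the fault an unqualified label and not a false statement. It does not make a one-session score a measure of the two-session condition.

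A reader might infer more than the documents support:
- *That the SFS could not respond on the day, so Hypothesis 2a was bound to be null.* The 67–78% share is inferred from domain names and depends on how they are classed. The documents give neither the items nor the recall window.
- *That carryover turns the test against active stimulation.* This needs a lasting effect. The visits are at least a week apart so that effects dissipate (Section 5), and Section 11.2 anticipates no lasting effect.
- *That half the stimulation means half the effect or a known loss of power.* No dose-response for the SFS is given.
- *That Q15 was left unreversed.* The documents state no reversal, but they do not show that it was omitted.

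**Conclusion.** The point holds as a mismatch between the hypothesis and the measurement. The SFS is completed after one of two sessions, and Section 9 does not say so. The Hypothesis 2a test estimates D − 0.52L: a same-day, one-session effect on self-report, less any persisting Visit 1 effect, which on the protocol's own expectation is small or absent. It is not evidence for or against the two-session condition, nor on its own for or against better daily-life functioning.

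The timing is explicit in the documents. The expression D − 0.52L assumes no period effect and nothing lasting from sham. No loss of effect or power is claimed. The paired test and the sample size stand.

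The EMA weeks follow both sessions of a visit, so Hypothesis 2b is the planned comparison that can address the full condition in daily life. That depends on the keying of Q15: if it was left unreversed, the composite moves by 0.67d for a uniform gain of d, and the standardized effect is 82–94% of the correctly scored one under the assumed correlations.

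**What to change.** 1. In Section 9, Hypothesis 2a, replace the timing phrase with: *completed once per stimulation visit, after the first of two sessions*.
2. Report the SFS result as same-day self-report after one session. Do not use it for or against an effect of the two-session condition or improved daily-life functioning.
3. Rest the daily-life part of Goal 2 on Hypothesis 2b. Report the EMA-active minus EMA-sham contrast explicitly, because the plan names three dummy-coded periods without stating the reference. Reverse-score Q15 (8 − Q15) before averaging it with Q4 to Q7 and Q14, or confirm that this was done.

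The cost is wording in Section 9 and the report, plus a scoring check and, if Q15 was not reversed, a rerun of the composite model. No new data are needed. The downside is that Hypothesis 2a supports a narrower claim, and the daily-life conclusion rests on EMA, where 47 of 50 participants have full data.

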371 stimulation condition relative to sham stimulation as measured by *EMA assessments* (i.e., more
372 interactions with others, more positive experience in, and expectations of, daily social
373 interactions).

374 4. Participants

375 A total of 62 participants (age = 18-64) diagnosed with schizophrenia or schizoaffective
376 disorder with current (in the past week) or recent (in the past month) paranoia were enrolled in
377 the study. Twelve participants withdrew ($n = 4$), were lost to follow-up ($n = 7$), or were
378 determined ineligible after the enrollment visit ($n = 1$), resulting in 50 participants completing
379 the whole procedure (see **Table 1** in the main article). Non-completers did not differ
380 significantly from the completed sample in age ($p = 0.813$), gender ($p = 0.693$), race ($p = 0.321$),
381 ethnicity ($p = 0.970$), IQ ($p = 0.322$), years of education ($p = 0.538$), handedness ($p = 0.861$), or
382 CPZ-equivalent ($p = 0.176$). However, a higher proportion of non-completers were not taking
383 any medications for their mental disorders ($n_{\text{Not-taking medication}} = 8$, 66.66% of the subsample)

384 compared to completers ($n_{\text{Not-taking medication}} = 3$, 6.00% of the subsample; $\chi^2 (1) = 24.41$, $p <$
385 0.001), suggesting a lower adherence to treatment and possibly more severe psychopathological
386 symptoms in this population. Supporting this notion, more non-completers showed current
387 paranoia ($n_{\text{current paranoia}} = 12$, 100.00% of the subsample) compared to completers ($n_{\text{current paranoia}} =$
388 38, 76.00% of the subsample; $\chi^2 (1) = 3.57$, $p = 0.059$) at a marginally significant level.

389 4.1 Sample Size Estimation

390 In our pilot study using an undergraduate sample, a medium effect size was revealed in
391 the active stimulation group (Cohen's $d = 0.51$), thus it was used for sample size estimation
392 using G*Power 3.1 (Faul et al., 2009) in the current study. For research goals 1 and 2, we
393 planned to use repeated-measures ANOVAs to test the tDCS effects on VLPFC on paranoia and
394 social functioning, and power analyses yielded a sample size of 46 in total ($\beta = 0.25$, power =

396 0.80, $\alpha = .05$, correlation among repeated measures = 0.3) in order to detect a medium effect.
397 Given the potentially high retention rate due to the repeated-stimulation characteristics of this

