791 and their ages when they moved (Oishi, 2010).

792 ***Social norm violation task (SNVT; Stimulation Visit 2).*** Recent studies investigating
793 how paranoia affects social decision-making found that paranoia was associated with decreased
794 cooperation and increased punishment towards partners in economic games (Raihani et al., 2021;
795 Raihani & Bell, 2018). In this study, we measured social norm violation perception to test its role
796 in paranoia and aggression. In this social norm violation task (Mu et al., 2015), participants rated
797 the appropriateness of 48 norm-violating behaviors (e.g., "John is talking on his cell phone in the
798 movie theater") on a 7-point scale (1 = strongly inappropriate, 7 = strongly appropriate). All
799 items were reverse-coded, and higher scores reflect being more critical towards the violation.

800 ***The Moralism Scale (MS; Stimulation Visit 2).*** The MS (Janoff-Bulman et al., 2009)

801 was used to further measure the perception of prescriptive (i.e., did not do the good thing, for
802 example, did not help others) and proscriptive (i.e., do the bad thing, for example, cheat or steal)
803 moral violation in the current study. The MS contains 20 scenarios where the character is
804 considering conducting a certain moral (violation) behavior or not (10 items for prescriptive
805 morality and 10 for proscriptive morality). Participants indicated whether the character in each
806 situation should or should not do the behavior on a 9-point scale (1 = feel very strongly he/she
807 should not do, 9 = feel very strongly he/she should). Scores were calculated for prescriptive and
808 proscriptive (will be reverse-coded) morality, respectively, with higher scores indicating a higher
809 weight has been assigned to prescriptive or proscriptive morality.

810 ***Aggression Questionnaire (AQ; Stimulation Visit 2).*** The AQ includes 29 items
811 assessing aggressive behavior and tendencies across 4 dimensions: physical aggression, verbal
812 aggression, anger, and hostility (Buss & Perry, 1992). It is rated on a 5-point scale ranging from
813 1 (extremely uncharacteristic of me) to 5 (extremely characteristic of me), with higher scores
814 indicating higher levels of aggression. In previous research, a significant positive correlation was
815 found between persecutory ideation and aggression reported via AQ in both individuals with
816 SSD and the general community (van Dongen et al., 2011).

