APPENDIX B: EMA QUESTIONS

Q1. Since the past alarm, how much have you had thoughts that you really can't trust other people?

(1 = not at all, 7 = very much)

Q2. Since the past alarm, how much have you been bothered by voices?

(1 = not at all, 7 = very much)

Q3. Since the past alarm, who have you interacted with? Select all that apply.

[haven't interacted with others; friends; spouse, partner, or other family; with roommates, co-workers, or others you know; with strangers; other people (please specify)]

Q4. How much interest or motivation did you have interacting with others since the last alarm?

(1 = not at all, 7 = very much)

Q5. How much pleasure or enjoyment did you feel in these interactions?

(1 = not at all, 7 = very much)

Q6. How did you feel toward others in the interactions?

(1 = on guard or threatened; 7 = trusting or warm)

Q7. What do you think others were thinking about you?

(1 = unlikeable or inferior; 7 = likeable or capable)

Q8. Since the past alarm, how much have you felt sad or depressed?

(1 = not at all, 7 = extremely)

Q9. Since the past alarm, how much have you felt energized or excited?

(1 = not at all, 7 = extremely)

Q10. Since the past alarm, how much have you been feeling like you belong or fit with others in your life?

(1 = not at all, 7 = extremely)

Q11. Since the past alarm, how much have you felt irritated or upset?

(1 = not at all, 7 = extremely)

Q12. Since the past alarm, how much have you felt that you were a burden on others?

(1 = not at all, 7 = extremely)

Q13. Since the past alarm, how much have you felt happy?

(1 = not at all, 7 = extremely)

Q14. How much interest or motivation do you have in interacting with others later today?

(1 = not at all, 7 = very much)

Q15. How much do you want to avoid others later today?

(1 = not at all, 7 = very much)

830 **References**

831 Adams, R. B., Gordon, H. L., Baird, A. A., Ambady, N., & Kleck, R. E. (2003). Effects of gaze
832 on amygdala sensitivity to anger and fear faces. *Science*, 300(5625), 1536–1536.
833 <https://doi.org/10.1126/science.1082244>

834

836 *Nature*, 393(6684), 470–474. <https://doi.org/10.1038/30982>

837

839 *Journal of Neuroscience*, 15(9), 5879–5891. <https://doi.org/10.1523/jneurosci.15-09-05879.1995>

841

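### As written, the Hypothesis 2b composite averages Q15 (wanting to avoid others) with five items scored in the opposite direction, and no reversal is stated

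*Combined protocol and SAP*

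**What the plan says.** Section 9, under Hypothesis 2b, models daily social functioning as two outcomes. Q3 is analysed alone because its range differs. The second outcome is "the average of items Q4, Q5, Q6, Q7, Q14, and Q15", which is "named as social interaction motivation and" experience. The only thing section 9 says about how these items compare is that "the remaining six items adhere to a score range of 1-7".

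Appendix B gives the wording. Two neighbouring items carry identical end labels (1 = not at all, 7 = very much):

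- "Q14. How much interest or motivation do you have in interacting with others later today"
- "Q15. How much do you want to avoid others later today"

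Section 3.1 sets the intended direction. After active stimulation, Hypothesis 2b predicts more "interactions with others, more positive experience in, and expectations of, daily social" interactions, so a higher composite is meant to be better.

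Elsewhere the document does state reversals. In Appendix A, for the social norm violation task, all "items were reverse-coded, and higher scores reflect being more critical towards the violation". The Moralism Scale gets scores for prescriptive and "proscriptive (will be reverse-coded) morality, respectively, with higher scores indicating a higher" weight on that type of morality. Sections 8 and 9 and Appendix B contain no such statement for Q15.

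**The concern.** A mean of several items measures one construct only if a high score has the same meaning on each item. Here five items rise as social functioning improves and one falls. A shared 1-7 range does not settle this, because range and direction are separate properties.

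If an analyst applies section 9 literally, a participant who wants to avoid others less receives a lower social functioning score. Two sets of answers can also be placed in the wrong order. One of the two Hypothesis 2b outcomes would then not measure what it is named for. The composite was assembled in section 9 itself and no outside scoring source is cited for it, so that sentence is its only scoring rule.

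**Working it through.** **The plan's own figure.** The plan states no figure for this composite. Its one computed design figure is the sample size of 46 in section 4.1. Reading the printed 0.25 as the effect size f, with correlation 0.3, α = 0.05 and two measurements, the noncentrality is 46 × 2 × 0.25² / (1 − 0.3) = 8.21 and the power is 0.801. So 46 reproduces, and this point does not affect it.

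**Inputs.** The composite rule is from section 9; the item wording and end labels are from Appendix B.

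| Item | Subject | A score of 7 is |
|---|---|---|
| Q4 | interest in interacting since the last prompt | favourable |
| Q5 | enjoyment of the interactions | favourable |
| Q6 | on guard (1) to warm (7) | favourable |
| Q7 | seen as inferior (1) to capable (7) | favourable |
| Q14 | interest in interacting later | favourable |
| Q15 | wish to avoid others later | unfavourable |

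**Scores.** Let S be the sum of Q4, Q5, Q6, Q7 and Q14. The score as written is (S + Q15)/6. Correctly keyed, it is (S + 8 − Q15)/6.

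| Answers | As written | With 8 − Q15 |
|---|---|---|
| Best: five 7s, Q15 = 1 | (35 + 1)/6 = 6.00 | (35 + 7)/6 = 7.00 |
| Worst: five 1s, Q15 = 7 | (5 + 7)/6 = 2.00 | (5 + 1)/6 = 1.00 |
| Five 5s, Q15 = 1 | (25 + 1)/6 = 4.33 | (25 + 7)/6 = 5.33 |
| Five 4s, Q15 = 7 | (20 + 7)/6 = 4.50 | (20 + 1)/6 = 3.50 |

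The span from worst to best is 4 points instead of 6. The last two rows change order.

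**Change scores.** A one-point fall in Q15 alone moves the mean by −1/6 = −0.17 instead of +0.17. An improvement of d on all six items moves it by (5d − d)/6 = 0.67d, so half a point on every item appears as 0.33.

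**Standardised effect (illustration only).** Assume equal item SDs, a common inter-item correlation r after correct keying, and Q15 moving m times as far as the other items. Relative to correct keying, the standardised effect is

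(5 − m)/(5 + m) × √[(6 + 30r)/(6 + 10r)].

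The square-root term is 1.00 at r = 0, 1.22 at 0.2, 1.34 at 0.4, 1.41 at 0.6 and 1.44 at 0.7. For r from 0 to 0.7 this gives:

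| Q15 movement relative to the others (m) | Ratio to correct keying |
|---|---|
| 0 | 1.00 to 1.44 |
| 0.5 | 0.82 to 1.18 |
| 1 | 0.67 to 0.96 |
| 2 | 0.43 to 0.62 |

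The documents give neither r nor m, and the ratio falls on both sides of 1.

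**Which correlation can reveal the keying.** Under the same common-r assumption, an unreversed Q15 correlates with the mean of the other five at −5r/√(5 + 20r). That is −0.19 at r = 0.1, −0.33 at 0.2 and −0.55 at 0.4. Its correlation with the six-item composite that contains it is (1 − 5r)/√(6 + 10r), or +0.19, 0 and −0.32 at the same values. The second can be positive with Q15 unreversed, so it can mislead.

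**The case against.** The strongest reply is that this is an omission in reporting and not a wrong rule. Section 9 is a short past-tense account and never says raw scores were averaged. The hypothesis has a clear direction, Q15 sits beside its mirror item Q14, and reversing such an item is routine. Silence on keying is also not peculiar to Q15: section 7.2 gives the State Social Paranoia Scale a 20-100 total that includes positive-thinking items without saying how they enter it. The 1-7 remark can fairly be read as explaining why Q3 is separate, not as a check that the six items may be averaged.

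Part of this stands. The text does not show that Q15 was analysed unreversed, and the explicit reversals in Appendix A are only weak evidence about what was done here. But section 9 does give a formula, and that formula followed literally produces the wrong score. This goes beyond missing detail.

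Three narrower objections have some force.

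- **Effect on sensitivity.** Its direction is undetermined. That is correct, and no power figure is claimed.
- **The ranking example.** It is said to compare different people, while Hypothesis 2b compares periods within people. The same two answer patterns could come from one person in two periods, so the arithmetic still applies, though how often this happens is unknown.
- **The correlation check.** It relies on a simple model. If some participants use the high end of every scale, an unreversed Q15 could correlate positively with the rest, so the check is indicative and the scoring code is decisive.

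**Conclusion.** The point holds: as written, the Hypothesis 2b composite is mis-keyed and should be corrected. Provided the rule is applied literally, these consequences need no further assumption: a worst-to-best range of 2 to 6 instead of 1 to 7, and a 0.17-point move in the wrong direction for each one-point fall in avoidance. The factor of 0.67 also requires that all six items improve equally. The effect on the standardised difference, and so on power, cannot be determined from the documents.

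The scope is one of the two Hypothesis 2b outcomes. Q3, the Hypothesis 1b analysis of Q1 and the in-lab outcomes are untouched. If Q15 was in fact reversed, the results stand and only the text needs correcting.

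**What to change.** In section 9, define the composite as the average of Q4, Q5, Q6, Q7, Q14 and reverse-scored Q15 (8 − Q15), with higher scores meaning better functioning.

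Then confirm from the scoring code what was done. If the code is unavailable, correlate Q15 as it entered the composite with the mean of the other five items. A negative value points to Q15 having been left unreversed. A positive value is reassuring but not proof. Do not use the correlation with the full six-item composite.

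Rerun the Hypothesis 2b composite model only if Q15 was left unreversed. The cost is one sentence, one check of the code and at most one model; no new data are needed.
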